# 3.8.3. Selection of Data in the Event of Multiple Records in an Analysis Window

Depending on the statistical analysis method, single values may be required for each analysis window. For example, change from baseline by visit usually requires a single value, whereas a time-to-event analysis would not require 1 value per analysis window. All values will be included in listings, but when a single value is required for analysis and table summarization the selection criteria listed below will apply.

If multiple valid, nonmissing, continuous measurements exist in an analysis window, records will be chosen based on the following rules if a single value is needed:

• In general, the baseline value will be the last nonmissing value on or prior to the first dosing date of study drug, unless specified differently. If multiple measurements occur on the same day, the last nonmissing value prior to the date of first dosing of study drug will be considered as the baseline value. If these multiple measurements occur at the same time or the time is not available, the average of these measurements (for continuous data) will be considered the baseline value.

For CASI questionnaires administered for (1) screening and (2) baseline visits, there should not be any instances of multiple screening or baseline records and such instances should be queried.

- For CASI Baseline questionnaires that still contain multiple records per subject ID after data query, the last record collected on or prior to the first dose date will be selected.
- For CASI Screening questionnaires that still contain multiple records per subject ID after data query, the last record collected prior to the first dose date will be selected.

For Alcohol Use Disorders Identification Test (AUDIT) questionnaires collected at screening only, there should not be any instances of multiple baseline records and such instances should be queried. For AUDIT questionnaires that still contain multiple records per subject ID after data query, the last record(s) collected on or prior to the first dose date will be selected.

## • For postbaseline visits:

For BMD data, the record(s) collected on the latest day in the window will be selected for analysis.

For CASI Follow-Up questionnaires, the record(s) collected on the day closest to the nominal day for that visit will be selected. If there are 2 days equidistant from the nominal day, the later day will be selected. Additionally, as some subjects retrospectively completed CASI questionnaires for previous missed visits, when multiple record(s) occur on the same day, the record with a subject assigned visit week equal to the analysis window visit week defined in Section 3.8.2 will be selected.

For Week 4 PK and PBMC trough samples, analysis windows will not be applied, but only samples labeled as a 'trough' collection will be selected. For anytime PK samples, only samples labeled as an 'anytime' collection will be selected and the rules below for other numeric observations applied.

For other numeric observations (ie, except BMD, CASI and Week 4 trough specified above), the record(s) collected on the day closest to the nominal day for that visit will be selected. If there are 2 days equidistant from the nominal day, the later day will be selected.

For any numeric observations, if there are multiple records on the selected day, the average will be taken.

If multiple valid nonmissing categorical measurements exist in a window, records will be chosen as follows:

- For baseline, the last available record on or prior to the first dose date of study drug will be selected. If there are multiple records with the same time or no time recorded on the same day, the value with the lowest severity will be selected (ie, normal will be selected over abnormal) except for gonorrhea and chlamydia laboratory STIs where the worst severity value will be selected (ie, abnormal will be selected over normal).
- For postbaseline visits, the worst severity value within the window will be selected (ie, abnormal will be selected over normal).

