The analysis windows for fasting glucose, lipids (including total cholesterol, high density lipoprotein [HDL], direct low density lipoprotein [LDL], and triglycerides), HBV serology (including HBsAb, HBsAg, and HBcAb) and HBV DNA assessments are presented in Table 3-2.

Table 3-2. Analysis Windows for Fasting Glucose, Lipids, HBV Serology and HBV DNA Assessments

Visit ID	Nominal Day	Lower Limit	Upper Limit
Baseline	1	(none)	1
Week 24	168	2	252
Week 48	336	253	420
Week 72	504	421	588
Week 96	672	589	756
Week 120	840	757	924
Week K (K is every 24 weeks after previous visit)	K*7	(K-12)*7+1	(K+12)*7

Fasting glucose and lipids (fasting not required at screening) include total cholesterol, HDL, total cholesterol to HDL ratio, direct LDL, and triglycerides from Covance central laboratory data.

The analysis windows for anytime PK, STI laboratory tests for gonorrhea, chlamydia and syphilis as well as syphilis diagnosis by the investigator are presented in Table 3-3.

Table 3-3. Analysis Windows for Anytime PK, STI Laboratory Tests and Syphilis Diagnosis by the Investigator

Visit ID	Nominal Day	Lower Limit	Upper Limit
Baseline	1	(none)	1
Week 12	84	2	126
Week 24	168	127	210
Week 36	252	211	294
Week 48	336	295	378
Week 60	420	379	462
Week 72	504	463	546
Week 84	588	547	630
Week 96	672	631	714
Week 108	756	715	798
Week 120	840	799	882
Week K (K is every 12 weeks after previous visit)	K*7	(K 6)*7+1	(K+6)*7

STI laboratory tests include Covance central laboratory tests and local laboratory tests for gonorrhea and chlamydia (urine, rectal swab and pharyngeal swab) as well as syphilis.

The analysis windows for HCV antibody (HCVAb) and HCV RNA are presented in Table 3-4.

Table 3-4. Analysis Windows for HCV Serology and HCV RNA Assessments

Visit ID	Nominal Day	Lower Limit	Upper Limit
Baseline	1	(none)	1
Week 48	336	2	504
Week 96	672	505	840
Week K (K is every 48 weeks after previous visit)	K*7	(K-24)*7+1	(K+24)*7

The analysis windows for DXA BMD are presented in Table 3-5. Subjects will have a DXA scan at the end of blinded treatment visit, in additional to the regular DXA scans at every 48 weeks, which may result in multiple assessments for a single analysis window. For post Week 144 visit, the value closest to the lower limit of its analysis window will be used for analysis. For other visits, values closest to the nominal visit will be used.

Table 3-5. Analysis Windows for DXA BMD

Visit ID	Nominal Day	Lower Limit	Upper Limit
Baseline	1	(none)	14

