Week 48	336	15	504
Week 96	672	505	840
Week 144	1008	841	1176
Post Week 144	(none)	1177	(none)

Note: The baseline value of DXA BMD is defined as the last value obtained on or prior to Study Day 14. For post Week 144, the value closest to the lower limit of its analysis window will be used for analysis.

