### 7.2.1. Summaries of Numeric Laboratory Results

Descriptive statistics will be provided by treatment group for each laboratory test specified in the study protocol as follows:

- Baseline values
- Values at each postbaseline analysis window
- Change from baseline at each postbaseline analysis window
- Percentage change from baseline to each postbaseline analysis window (if specified)

A baseline laboratory value will be defined as the last nonmissing value obtained on or prior to the date of first dose of study drug. Change from baseline to a postbaseline visit will be defined as the postbaseline value minus the baseline value. The mean, median, Q1, Q3, minimum, and maximum values will be displayed to the reported number of digits; SD values will be displayed to the reported number of digits plus 1.

In the case of multiple values in an analysis window, data will be selected for analysis as described in Section 3.8.3.

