### 7.3.1. Percentage Change from Baseline in Hip and Spine Bone Mineral Density

Percentage change from baseline in hip and spine BMD at Week 48 using observed on-treatment data are 2 of the 6 key (α-controlled) secondary endpoints.

The percentage change from baseline in hip BMD and spine BMD will be summarized for on-treatment data (ie, data collected up to 30 days after permanent discontinuation of study drug or all available data for subjects who were still on study drug) using observed data by treatment group and visit using descriptive statistics for subjects in the Hip and Spine DXA Analysis Sets, respectively, and compared between the 2 treatment groups at each visit using ANOVA, which includes baseline F/TDF for PrEP and treatment as fixed effects.

As a sensitivity analysis, hip BMD and spine BMD based on on-treatment data using the LOCF and BIOCF methods will be summarized using the Hip and Spine DXA Analysis Sets.

Median (Q1, Q3) and mean (95% CI) of the percentage change from baseline in hip BMD and spine BMD over time using observed data will be plotted by treatment group. Listings of hip and spine DXA results will be provided.

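### Two SAP rules for choosing among BMD scans in one window contradict each other, and nothing says which governs; Week 96 hip and spine BMD is mainly affected

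*SAP*

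**What the plan says.** SAP Section 3.8.2 introduces the DXA windows (Table 3-5) by noting that participants have a scan at the end of blinded treatment on top of the 48-weekly scans, "which may result in multiple assessments for a single analysis window". It then settles the choice. For the last window, "For post Week 144, the value closest to the lower limit of its analysis window will be used for analysis" (from the note under Table 3-5, repeating the text). For the rest, "For other visits, values closest to the nominal visit will be used".

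SAP Section 3.8.3 deals with multiple records in a window and opens by saying that "when a single value is required for analysis and table summarization the selection criteria listed below will apply". Its item for postbaseline visits reads "For BMD data, the record(s) collected on the latest day in the window will be selected for analysis". The closest-to-nominal rule in the same list then leaves BMD out: "For other numeric observations (ie, except BMD, CASI and Week 4 trough specified above".

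Hip and spine BMD are "compared between the 2 treatment groups at each visit using ANOVA" (SAP Section 7.3.1). Week 96 hip and spine BMD is an other secondary endpoint, outside the alpha-controlled set (Protocol Sections 3.1.2 and 8.1.3).

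**The concern.** For any window holding two scans, the sections give different answers, and after Week 144 they give opposite ones (earliest against latest). A prespecified plan should define one record per participant and visit, and here it does not.

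What is at stake is what Week 96 BMD means. If the latest scan is taken, some participants contribute a measurement made well after Week 96 while others contribute one made on schedule, so the visit mixes exposure times. The clinical-status and graded-change summaries in SAP Sections 7.3.2 and 7.3.3 depend on the same choice of record.

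**Working it through.** **1. Windows.** Table 3-5 follows nominal day = 7K and upper limit = 7(K + 24); from Week 96 on, the lower limit is 7(K − 24) + 1.

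- K = 96: nominal 672, window 505–840.
- K = 144: nominal 1008, window 841–1176.
- K = 48: nominal 336, upper limit 504 (the lower limit of 15 follows the baseline window).

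All agree with the table.

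**2. The rules side by side.** Take a participant scanned on days 672 and 800, both in the Week 96 window.

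| Rule | Record chosen |
|---|---|
| 3.8.2, closest to nominal | day 672 |
| 3.8.3, latest day | day 800 |

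**3. Search for precedence.** Section 3.8.2 has the claim of being written for exactly this case. Section 3.8.3 has the claim of its opening sentence and of its explicit exemption of BMD. Neither refers to the other's BMD rule. SAP Section 7.2.1 sends laboratory data to Section 3.8.3 ("In the case of multiple values in an analysis window, data will be selected for analysis as described in Section 3.8.3"), and Section 7.5 does the same for weight and vital signs. Section 7.3 (BMD), Section 7.8 (changes from protocol) and the DXA programming specification (Appendix 12, item 17) contain no selection rule.

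**4. Size of the shift.** The latest record the Week 96 window admits is (840 − 672)/7 = 24 weeks after nominal. Protocol Section 6.10 allows scans within 6 weeks of the visit, so an on-schedule scan can be as early as day 630. Measured from there, the gap is (840 − 630)/7 = 30 weeks.

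**5. How many participants.** The documents give no DXA accrual curve, no scan dates and no lag between the last participant's Week 96 and the end-of-blinded visits (Protocol Section 6.4 says only that these follow notification). The following is therefore a scenario, not an estimate.

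SAP Appendix 9 (DBS 1.1) puts enrollment from September 2016 to June 2017. The span S is between 244 days (30 September to 1 June, 34.9 weeks) and 302 days (1 September to 30 June, 43.1 weeks), rounded to 35 and 43 weeks. Someone enrolled u weeks before the last participant has the end-of-blinded scan at Week 96 + u + L, where L is the lag in weeks. It falls in the Week 96 window when u + L ≤ 24. With u uniform on (0, S), scans on the visit day and everyone still on drug, the share with two scans in the window is max(0, 24 − L)/S:

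| Lag L (weeks) | S = 35 | S = 43 |
|---|---|---|
| 0 | 24/35 = 68.6% | 24/43 = 55.8% |
| 6 | 18/35 = 51.4% | 18/43 = 41.9% |
| 12 | 12/35 = 34.3% | 12/43 = 27.9% |
| 18 | 6/35 = 17.1% | 6/43 = 14.0% |
| 24 or more | 0% | 0% |

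Two scans do not always mean two answers. Simulating the Week 96 scan as uniform within ±6 weeks, the rules choose different scans in about 49–60% at zero lag. If the end-of-blinded scan also varies by ±6 weeks, and scans after that visit are excluded as open-label data, the figures are roughly 25–30% at zero lag, 17–21% at 12 weeks, about 4% at 24 weeks and 0% at 30 weeks.

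**6. Week 48.** A second scan in this window needs an interruption or early-discontinuation scan. The latter is taken only if more than 12 weeks have passed since the previous scan (Protocol Section 6.10). With the scheduled scan on day 336, that means after 336 + 84 = 420, so on days 421–504. The documents give no count.

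**The case against.** The strongest reply is that a sensible programmer would follow Section 3.8.2. It names the end-of-blinded scan, explains the duplication and states the choice, whereas Section 3.8.3 offers one line in a general list. That supports keeping the 3.8.2 rule, but it does not make the SAP unambiguous. Section 3.8.3 claims authority whenever a single value is needed, and it excludes BMD from its closest-day rule by name, which looks deliberate.

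A second reply is that the 69% ceiling flatters the problem. This largely stands. That figure counts double scans at zero lag with every scan on its visit day, and the fuller simulation gives less than half of it. The post-Week 144 row in Table 3-5 also hints at a long lag. The first participant enrolled reaches day 1177 by the end-of-blinded visit only if L is about (1177 − 672)/7 − S = 72.1 − S, that is 29 weeks (S = 43) to 37 weeks (S = 35), and at such lags the Week 96 overlap is essentially nil. The row may, however, be merely defensive.

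Third, the consequences are limited: Week 96 BMD is not alpha-controlled, both arms are treated alike, and all values appear in listings. That is correct, and it is why the point does not threaten the trial's conclusions.

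Finally, SAP Section 2.3 describes the end-of-blinded analysis in the past tense, although Section 1 is prospective, so a text edit may come too late. The fix allows for this.

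**Conclusion.** The contradiction is established from the text alone and does not depend on any scenario: two BMD-specific rules select different records, and no passage ranks them. It should be fixed.

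Its practical reach is uncertain. The affected share at Week 96 lies between 0% and about 69%. The upper end requires uniform accrual over 35 weeks, a DXA subset enrolled like the whole trial, scans on the visit day, no one off drug and no lag. Realistic scan dates and open-label exclusions lower it considerably. Alpha-controlled Week 48 BMD can be touched only through interruption or early-discontinuation scans, in unknown number. The size and direction of any change in the BMD results cannot be computed from the documents, and no bias towards either arm is shown.

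**What to change.** In SAP Section 3.8.3, delete the latest-day sentence for BMD, remove BMD from the exemption in the rule for other numeric observations, and cross-refer to Section 3.8.2 (closest to the nominal visit; closest to the lower limit after Week 144). Section 3.8.2 has no tie-break, so add one as new text: the later day if two scans are equidistant, as Section 3.8.3 already does for other numeric data. State the same rule in Appendix 12, item 17, and confirm that it matches the rule used for Week 48 BMD in the primary analysis.

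If the end-of-blinded analysis has already been run, report which rule was applied, give the number of participants per arm with more than one scan in a window, and present the other rule as a sensitivity analysis.

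The cost is two text edits, one cross-reference and one new sentence in Section 3.8.3, plus one line in Appendix 12. If the analysis has been run, add one count per arm and one table. No new data are needed.

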## 4. SUBJECT DISPOSITION

## 4.1. Subject Enrollment and Disposition

## 4.1.1. Subject Enrollment

Subject enrollment has already been summarized in the primary analysis and will not be repeated in this analysis.

# 4.1.2. Subject Disposition

The summary of subject disposition will be provided by treatment group and overall for all screened subjects. This summary will include the number of subjects screened, screen failure subjects who were not randomized, subjects who met all eligibility criteria and were not randomized, subjects randomized but never treated, subjects who were HIV positive at screening, subjects in the Safety Analysis Set, and subjects in the FAS, as applicable.

In addition, the number and percentage of the subjects in the following categories will be summarized:

- Still on study drug in the DB phase, if applicable
- Completing study drug in the DB phase
- Prematurely discontinuing study drug in the DB phase (with summary of reasons for discontinuing study drug)
- Still on study in the DB phase, if applicable
- Completing study in the DB phase (see Appendix 11)
- Prematurely discontinuing from study in the DB phase (with summary of reasons for discontinuing study)
- Entering in the OLE phase

The denominator for the percentages of subjects in each category will be the number of subjects in the Safety Analysis Set. Separate summaries of subject disposition in each category by treatment group and overall will include subjects in the Hip or Spine DXA Analysis Sets.

No inferential statistics will be generated. A data listing of reasons for premature study drug/study discontinuation will be provided.

# 4.2. Extent of Study Drug Exposure and Adherence

# 4.2.1. Duration of Exposure to Randomized Study Drug

Duration of exposure to study drug will be defined as (the DB phase last dose date—the DB phase first dose date + 1), regardless of temporary interruptions in study drug administration, and will be expressed in weeks using up to 1 decimal place (ie, 4.5 weeks). If subjects have not permanently discontinued study drug (whether still on the randomized study drug or on a study drug interruption) at the time of the data cut date, the latest of study drug start dates and end dates, the clinic visit or laboratory visit dates excluding the 30-day follow-up visit date, will be used to impute the last dose date for the calculation of the duration of study drug exposure.

Duration of exposure to randomized study drug will be summarized using descriptive statistics (n, mean, SD, median, Q1, Q3, minimum, maximum and the total person-years of exposure) and as the number and percentage of subjects exposed for specified periods, ie,  $\geq$  4 weeks (28 days),  $\geq$  8 weeks (56 days),  $\geq$  12 weeks (84 days),  $\geq$  24 weeks (168 days),  $\geq$  36 weeks (252 days),  $\geq$  48 weeks (336 days),  $\geq$  60 weeks (420 days),  $\geq$  72 weeks (504 days),  $\geq$  84 weeks (588 days),  $\geq$  96 weeks (672 days),  $\geq$  108 weeks (756 days),  $\geq$  120 weeks (840 days),  $\geq$  132 weeks (924 days),  $\geq$  144 weeks (840 days), etc.

Summaries will be provided by treatment group and overall for subjects in the Safety Analysis Set and Hip or Spine DXA Analysis Sets. No inferential statistics will be provided.

Time to premature discontinuation of randomized study drug will be analyzed using the Kaplan-Meier (KM) method by treatment group based on the Safety Analysis Set. The log rank test will be used to compare the difference in time to premature study drug discontinuation between the 2 treatment groups. Subjects who have not prematurely discontinued study drug (whether still on the randomized study drug or on a study drug interruption) at the time of the data cut date will be censored on the imputed last dose date as defined in this section. A plot of KM estimates for the time to premature discontinuation of study drug by treatment group will be generated.

#### 4.2.2. Duration of Study Drug Holidays and Study Drug Interruptions

## 4.2.2.1. Definition of Study Drug Holidays and Study Drug Interruptions

The duration of study drug holidays and study drug interruptions will only be calculated for the randomize phase study drug. Study drug holidays or other study drug interruptions may occur when subjects cease taking study drug either with or without prior notification to the study sponsor and prior to permanently discontinuing study drug. For subjects who notified the study sponsor of their intention to take a study drug holiday and received pre-approval preceding the end of the interruption, records with '0' tablets administered are entered in the Study Drug Administration eCRF. Other study drug interruptions are defined as gaps in consecutive stop and start dates of study drug records with ≥1 tablet administered in the study drug administration eCRF.

During the DB phase, if subjects are on a study drug holiday or other study drug interruption at the time of the data cut date, the latest of study drug start dates and end dates, the clinic visit or laboratory visit dates during the DB phase, excluding the 30-day follow-up visit date, will be used to impute the end of the interruption for the calculation of the duration of study drug holiday or study drug interruption.

For the DB phase, durations of (1) study drug holidays, (2) other study drug interruptions and (3) any study drug interruptions (the cumulative total of both study drug holidays and other study drug interruptions) will be summarized using descriptive statistics (n, mean, SD, median, Q1, Q3, minimum, and maximum) and as the number and percentage of subjects with study drug holidays and/or other study drug interruptions for specified periods, ie,  $\geq$  4 weeks (28 days),  $\geq$  8 weeks (56 days),  $\geq$  12 weeks (84 days),  $\geq$  24 weeks (168 days),  $\geq$  36 weeks (252 days),  $\geq$  48 weeks (336 days),  $\geq$  60 weeks (420 days),  $\geq$  72 weeks (504 days),  $\geq$  84 weeks (588 days),  $\geq$  96 weeks (672 days), etc. Multiple study drug holidays and/or interruptions per subject will be combined into one cumulative total duration of study drug holidays and/or interruptions for each subject.

# 4.2.2.2. Incomplete Dates

If study drug end or restart dates are incomplete (month and year only), then the day for the computation of study drug interruption durations will be imputed as the 15th of the month. However, if the study drug end and restart dates occur in the same month and year and at least one is incomplete (month and year only), then an interruption duration of 15 days will be imputed. If study drug end and restart dates are completely missing or only year is available, data query is needed and no interruption duration will be imputed.

